**Please save frequently**

- b) Describe any animal experimentation and findings leading to the formulation of the study, if there is no supporting human data.

N/A

## 2. Purpose of the study

- a) Provide a brief lay summary of the project in <200 words. The lay summary should be readily understandable to the general public.

Our study is a prospective comparison between absorbable hemostatic agents as a group and the body's natural hemostatic ability without aid of therapy in patients undergoing bilateral sinus surgery with or without septoplasty.

Page numbers from a sponsor's protocol/grant may be referenced in 2b and 2c.

- b) List your research objectives (specific aims & hypotheses of the study).

The purpose of this study is to evaluate the efficacy of absorbable hemostatic agents in comparison with physiologic hemostasis after endoscopic sinus surgery. We aim to determine the relative efficacy of hemostatic agents to halt epistaxis and compare this with the degree of epistaxis observed without therapy. Also will evaluate objective healing parameters.

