**1. Background**

**Protocol Title:** Analysis of hemostatic agents compared to physiologic hemostasis

---

Page numbers from a sponsor's protocol/grant may be referenced in 1a and 1b.

- a) **Provide an introduction and background information. Describe past experimental and/or clinical findings leading to the formulation of the study, if applicable. Investigator Initiated studies must cite references in the response provided or attach a bibliography. *\*?HELP?\****

In this study we wish to determine if the use of hemostatic agents after endoscopic sinus surgery is superior to no agent at all. We will treat patients with one of many different FDA approved hemostatic agents in one of their nostrils and compare it to a side in which no therapy is applied. We will then evaluate qualities of the patient's recovery (synechia formation, granulation, edema, infection, and time spent debriding the sinuses) in response to intervention.

Functional endoscopic sinus surgery (ESS) is a safe, commonly performed procedure primarily in an outpatient setting. One of the most prevalent complications is post-operative epistaxis. To prevent this nasal packing is often employed. Traditionally non-absorbable packing was employed; yet, this has fallen out of favor with most otolaryngologists considering the great discomfort of the packing, especially upon removal (von Schoenberg). In addition to this, with removal of non-absorbable packing interruption of the wound bed is inevitable. This has led to a paradigm shift towards absorbable packing, which are biomaterials that provide substrate to stimulate clotting. Absorbable hemostatic agents tend to spare the mucosa and are less painful upon removal (Maccabee). However, absorbable packing comes with the possible drawback of increased rates of synechia formation secondary to initiation of local inflammation (Valentine). Standard of care is no packing, one of these types of absorbable packing, or removing packing.

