**Please save frequently**

- c) Describe the study design (e.g., single/double blind, parallel, crossover, control, experimental, observational, etc.). If the study is investigator-initiated, a timeline for individual subject recruitment, follow-up, and analysis for the study is required. Also, indicate if the subjects will be randomized.

Our study is a prospective comparison between absorbable hemostatic agents as a group and the body's natural hemostatic ability without aid of therapy in patients undergoing bilateral sinus surgery with or without septoplasty.

We calculated the sample size and power analysis in the following way:

Given the number of statistical tests, we calculated a Bonferonni correction to set the alpha for the analysis at 0.017 (alpha originally at .05 divided by the number of tests = .05/30 = 0.017). Using G-Power statistical software, power analyses were completed using the Means: Wilcoxon-Mann-Whitney test (two groups). Given alpha at 0.017 and Power at 0.80, we determined that a total of 244 participants (122 in the control group, 122 in the hemostatics group) would be needed to detect a medium effect size (d=0.5). Since one nostril will be used as the control and the therapy applied to the other side, the number of participants needed drops to 122.

Based on previous studies, we conservatively expect a dropout rate of 15%. In order to maintain the same number of participants, we would need to enroll a total of 144 participants

Postoperatively, patients will rate subjective symptoms such as nasal obstruction, bleeding,

**Protocol Title:** Analysis of hemostatic agents compared to physiologic hemostasis

---

pain, and nasal discharge on a scale ranging from 1-10, of which 10 is the most severe. Similarly, the treating physicians on endoscopic examinations will rate objective measures such as mucosal edema, infection, time spent debriding, and synechiae formation. (Please see the attached patient and physician questionnaires) Patient questionnaires will be completed on postoperative days #1, 2, 7, and 14. Surgical healing outcomes will be noted during routine postoperative visits 1 and 2 weeks after surgery. Expected total duration of each subjects' participation is 6 weeks. Total subject accrual should take no longer than one year. Data analysis will take up to three months. Estimated time of completion is 03/2018.

d) **If subjects will be given placebo, please justify placebo use. \*?HELP?\***

N/A

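### Bleeding is the first stated aim, but alpha is divided over 30 unlisted tests and no primary outcome, time point or success rule is named; the power cost depends on which alpha, sidedness and correlation apply

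*Combined protocol and SAP*

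**What the plan says.** Section 2b gives the aim as to "determine the relative efficacy of hemostatic agents to halt epistaxis and compare this with the degree of epistaxis observed without therapy" and continues: "Also will evaluate objective healing parameters". The title and the lay summary (2a) are also about hemostasis. The background (1a) asks whether agents are superior to none, but the outcomes it then lists are "synechia formation, granulation, edema, infection, and time spent debriding the sinuses", without bleeding.

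Section 2c states that "we calculated a Bonferonni correction to set the alpha for the analysis at 0.017" and shows the sum as "alpha originally at .05 divided by the number of tests = .05/30 = 0.017". One sample size follows, "Given alpha at 0.017 and Power at 0.80", for d = 0.5 with a two-group Wilcoxon-Mann-Whitney test: 122 per group, then taken as 122 patients because each patient supplies both sides, and 144 after 15% dropout. The effect size is tied to no outcome, and sidedness is not stated.

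Section 3d plans a non-parametric ANOVA of the patient and physician data with post-hoc multiple comparisons. Neither 2c nor 3d names a primary outcome, a time point or a testing order. Section 3c asks for efficacy and futility guidelines; the answer covers only the handling of side effects.

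**The concern.** Section 9.7 promises a definitive answer on whether hemostatic agents beat no treatment, but nothing says which result would be that answer. Bleeding is one of four patient-rated symptoms, each rated on several days, alongside five physician-rated measures at several visits. With an equal Bonferroni share for each of 30 tests, the question placed first in 2b gets one thirtieth of the available alpha. If some ratings favour the agents and others do not, the plan has no rule for calling the trial positive or negative. Two things are at stake: power on the bleeding question, and an agreed reading of mixed results.

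**Working it through.** **1. Is there a list of 30?** Counting only named items, 2c gives 4 symptoms × 4 days + 4 physician measures × 2 visits = 24. Section 3b gives 4 × 5 days + 5 × 3 visits = 35. A mix of the two (4 × 5 + 5 × 2) gives 30, but the plan does not say that this is its count.

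**2. Which alpha was used?** 0.05/30 = 0.00167; 0.017 is 0.05/3. To see which one the sizing used, take the Wilcoxon-Mann-Whitney test by asymptotic relative efficiency with a normal parent: effective n per group n' = n × 3/π, noncentrality d√(n'/2), noncentral t on 2n' − 2 degrees of freedom, d = 0.5, power 0.80.

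| Alpha | One-sided n per group | Two-sided n per group |
|---|---|---|
| 0.00167 | **122** | 136 |
| 0.017 (as printed) | 75 | 89 |
| 0.05 (single test) | 53 | 67 |

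Only one-sided 0.00167 gives the plan's 122. For dropout, 122/0.85 = 143.5, so 144, which matches. The sizing therefore did divide alpha by 30, and 0.017 looks like a decimal slip.

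**3. Power at 122, sides treated as uncorrelated (the plan's own unpaired method), d = 0.5.** Here n' = 122 × 3/π = 116.5 and the noncentrality is 0.5 × √(116.5/2) = 3.82.

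| Alpha | One-sided | Two-sided |
|---|---|---|
| 0.00167 | 80.1% | 73.6% |
| 0.017 | 95.3% | 92.0% |
| 0.05 | 98.5% | 96.7% |

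Against a single test at 0.05, the loss is 18.4 points (one-sided) or 23.1 points (two-sided) at 0.00167. At 0.017 it is 3.2 or 4.7 points.

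**4. Paired test, 122 pairs, two-sided.** dz = d/√(2(1 − ρ)), noncentrality dz√n', n' − 1 degrees of freedom. The documents give no within-patient correlation ρ, so the ρ values are assumptions; d = 0.3 is also an assumption.

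| d | ρ | dz | Power at 0.00167 | Power at 0.05 | Loss (points) |
|---|---|---|---|---|---|
| 0.5 | 0 | 0.354 | 72.3% | 96.6% | 24.3 |
| 0.5 | 0.3 | 0.423 | 90.6% | 99.5% | 8.9 |
| 0.5 | 0.5 | 0.500 | 98.4% | almost 100% | under 2 |
| 0.3 | 0.5 | 0.300 | 51.0% | 89.5% | 38.5 |

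**5. Family-wise error over 30 independent tests.** At 0.017: 1 − (1 − 0.017)^30 = 40.2%. At 0.00167: 1 − (1 − 0.00167)^30 = 4.9%.

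**The case against.** Four counter-arguments have weight.

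- **The trial was sized for the split alpha.** At its own d = 0.5 and one-sided, the plan keeps a conventional 80%. Two nostrils of one patient, selected for similar disease on both sides, are likely to be positively correlated, and a paired test would then recover much of the loss. A reader might infer that power on bleeding is far too low whatever is assumed; the documents do not support that. However, they specify neither a paired test nor a correlation, and the loss stays large if the true effect is below 0.5.
- **Bleeding first is not beyond dispute.** It rests on 2b, its word for adding healing, the title and the lay summary. The background puts only healing outcomes after its superiority question. A reader might infer that the sponsor has no choice left to make. It has one, and bleeding is the choice that best fits the objectives section.
- **Scattered significant results are not automatically false.** At a true 0.05/30, Bonferroni holds family-wise error at 5%, so each significant result is a valid claim about its own outcome. What is missing is a definition of overall success. The argument fails if 0.017 is the level applied.
- **It may be late.** The Expedited Paragraphs section marks the remaining activity as data analysis only. A primary named now may follow sight of the data. This limits how the fix may be described, but the gap remains.

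**Conclusion.** The point holds in a limited form. That no primary outcome, time point or success rule is named can be read directly from 2b, 2c and 3d, and rests on no assumption. The size of the power cost is conditional. It is 18 to 23 points at d = 0.5 if alpha is 0.05/30 and the sides are analysed as uncorrelated, and about 9 or under 2 points for a two-sided paired test at assumed correlations of 0.3 or 0.5. It rises to 38.5 points at an assumed d = 0.3 with correlation 0.5. At the printed 0.017 little power is lost (3 to 5 points in the uncorrelated calculation), but error control over 30 tests is. So either reading of the alpha needs repair. All power figures assume normally distributed ratings, through the 3/π efficiency, and a generic d that is not shown to apply to any particular bleeding summary.

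**What to change.** In 2b, 2c and 3d:

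1. Name one primary outcome that follows the stated aim: the treated-minus-untreated difference in patient-rated bleeding, summarised over stated post-operative days and excluding day 0 (2c lists days 1, 2, 7 and 14; 3b adds day 0). Test it once with a paired test at two-sided 0.05, and state that this result decides success.
2. Confirm that bleeding is rated separately for each side. Neither 2c nor 3b says so, and the questionnaires are attachments not included here. Without side-specific ratings this primary cannot be computed.
3. List the other symptoms and all healing outcomes as secondary, with Holm adjustment at the correct alpha. Test them for confirmatory claims only after the primary succeeds, or else report them as supportive.
4. Correct 0.017, and state the sidedness and the number of tests.
5. Date the change and state whether outcomes by side have already been seen. If they have, label the choice post hoc.

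This is a change of wording and analysis. It needs no new patients or visits, and no new data if the ratings are side-specific. The cost is that the healing outcomes, which the background also lists as study outcomes, become formally secondary.

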**Please save frequently**

- c) Describe the study design (e.g., single/double blind, parallel, crossover, control, experimental, observational, etc.). If the study is investigator-initiated, a timeline for individual subject recruitment, follow-up, and analysis for the study is required. Also, indicate if the subjects will be randomized.

Our study is a prospective comparison between absorbable hemostatic agents as a group and the body's natural hemostatic ability without aid of therapy in patients undergoing bilateral sinus surgery with or without septoplasty.

We calculated the sample size and power analysis in the following way:

Given the number of statistical tests, we calculated a Bonferonni correction to set the alpha for the analysis at 0.017 (alpha originally at .05 divided by the number of tests = .05/30 = 0.017). Using G-Power statistical software, power analyses were completed using the Means: Wilcoxon-Mann-Whitney test (two groups). Given alpha at 0.017 and Power at 0.80, we determined that a total of 244 participants (122 in the control group, 122 in the hemostatics group) would be needed to detect a medium effect size (d=0.5). Since one nostril will be used as the control and the therapy applied to the other side, the number of participants needed drops to 122.

Based on previous studies, we conservatively expect a dropout rate of 15%. In order to maintain the same number of participants, we would need to enroll a total of 144 participants

Postoperatively, patients will rate subjective symptoms such as nasal obstruction, bleeding,

**Protocol Title:** Analysis of hemostatic agents compared to physiologic hemostasis

---

pain, and nasal discharge on a scale ranging from 1-10, of which 10 is the most severe. Similarly, the treating physicians on endoscopic examinations will rate objective measures such as mucosal edema, infection, time spent debriding, and synechiae formation. (Please see the attached patient and physician questionnaires) Patient questionnaires will be completed on postoperative days #1, 2, 7, and 14. Surgical healing outcomes will be noted during routine postoperative visits 1 and 2 weeks after surgery. Expected total duration of each subjects' participation is 6 weeks. Total subject accrual should take no longer than one year. Data analysis will take up to three months. Estimated time of completion is 03/2018.

d) **If subjects will be given placebo, please justify placebo use. \*?HELP?\***

N/A

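### The Bonferroni alpha is misprinted (0.05/30 is 0.0017, not 0.017) and has no stated sidedness; once corrected, Holm's procedure would be a free, modest gain over it

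*Combined protocol and SAP*

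**What the plan says.** Section 2c (study design, sample size and power) applies one fixed threshold to every test: "we calculated a Bonferonni correction to set the alpha for the analysis at 0.017". The arithmetic is printed: "alpha originally at .05 divided by the number of tests = .05/30 = 0.017". The sample size is then tied to it: "Given alpha at 0.017 and Power at 0.80", with a standardised effect of 0.5 and G-Power's two-group Wilcoxon-Mann-Whitney option, the plan reports 244 in total, 122 per group. It then moves to a within-patient count: "Since one nostril will be used as the control and the therapy applied to the other side, the number of participants needed drops to 122". With 15% dropout this becomes 144 enrolled. Section 2c does not say whether the tests are one- or two-sided.

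Section 3d (data analysis) plans a non-parametric ANOVA with post-hoc multiple comparisons. It names no alpha and no correction. Neither section lists the 30 tests, names a primary outcome or gives a correlation between outcomes.

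**The concern.** Two things are at stake, and the order matters.

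- **Error control.** The name of the method and the printed formula both describe Bonferroni over 30 tests, but the printed result is ten times too large. An analyst who applies 0.017 as written would not hold the family-wise error at 5%. An analyst who recomputes 0.05/30 would use a threshold other than the one printed for the power calculation.
- **Efficiency.** Once the alpha is right, the plan is a single-step Bonferroni rule. Holm's procedure controls the same family-wise error under any dependence and rejects everything Bonferroni rejects, sometimes more. With 30 outcomes and no hierarchy among them, single-step Bonferroni can miss real effects that Holm would declare at no extra error.

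**Working it through.** **Inputs from section 2c:** overall alpha 0.05; 30 tests; printed per-test alpha 0.017; power 0.80; d = 0.5; 122 per group; dropout 15%. **Assumed, because the documents are silent:** sidedness, the number of true effects, the correlation between tests, and a normal parent distribution for the Wilcoxon-Mann-Whitney calculation.

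**1. The alpha.** 0.05/30 = 0.00167. The printed 0.017 is about 0.05/3.

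**2. Family-wise error, all nulls true.**
- At 0.017, independent tests: 1 − (1 − 0.017)^30 = 0.402. The upper bound under any dependence is 30 × 0.017 = 0.51. Simulated with equal correlation between tests: 0.32 at 0.3, 0.23 at 0.5, 0.15 at 0.7.
- At 0.00167, independent tests: 1 − (1 − 0.00167)^30 = 0.049.

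**3. Reproducing 122 per group.** The method uses the asymptotic relative efficiency 3/π = 0.955, a noncentral t with 2n(3/π) − 2 degrees of freedom, and noncentrality d√(n(3/π)/2). At n = 122 the noncentrality is 0.5 × √(122 × 0.955/2) = 3.82.

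| Alpha | One-sided n per group | Two-sided n per group |
|---|---|---|
| 0.017 (as printed) | 75 | 89 |
| 0.05/30 | **122** | 136 |

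Other parent distributions at 0.017 give 48 to 83 one-sided and 57 to 99 two-sided, so none reaches 122. Two-sided at 0.05/30, power at 122 per group is 0.736. The dropout step reproduces: 122/0.85 = 143.5, rounded up to 144.

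**4. Holm's thresholds.** Step k compares the k-th smallest p-value with 0.05/(31 − k): 0.00167, 0.00172, ..., 0.0125 (step 27), 0.01667 (step 28), 0.025, 0.05. The first step equals a correct Bonferroni. Holm is stricter than 0.017 at 28 of the 30 steps.

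**5. Power per true effect.** Simulation of 30 two-sided z-tests with noncentrality 3.82 for each true effect, 40,000 replicates. The row for 20 true effects comes from a companion simulation of 20,000 trials: 122 pairs, standardised paired difference 0.354, which is d = 0.5 with uncorrelated sides.

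| True effects | Correlation | Bonferroni at 0.05/30 | Holm | Gain (points) |
|---|---|---|---|---|
| 1 | 0 | 0.751 | 0.751 | 0 |
| 5 | 0 | 0.750 | 0.760 | 1.0 |
| 10 | 0 | 0.750 | 0.774 | 2.4 |
| 10 | 0.7 | 0.749 | 0.768 | 1.9 |
| 15 | 0 | 0.750 | 0.791 | 4.1 |
| 20 | 0.4 | 0.751 | 0.806 | 5.5 |
| 30 | 0 | 0.750 | 0.911 | 16.1 |
| 30 | 0.5 | 0.748 | 0.865 | 11.7 |

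Holm's simulated family-wise error stayed at 0.05 or below. The fixed 0.017 gives power of about 0.92 per effect in the same runs, but only with the inflated error in step 2. The Bonferroni column is near 0.75 rather than 0.736 because it uses a normal rather than a t approximation.

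**The case against.** The strongest objection is that a correctly computed Bonferroni is valid and standard. Choosing it is not an error, and the real defect here is the decimal. That stands: the alpha must be corrected first, and Holm is a refinement on top of it. Bonferroni also gives simpler simultaneous confidence intervals and one fixed threshold for planning. The plan mentions no such intervals, so that cost is small.

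A reader might infer several stronger things that the documents do not support:

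- *That the plan as printed wastes power.* It does not. At 0.017 it is too lenient, and moving to Holm would lower nominal power from about 0.92 while restoring error control.
- *That Holm helps because the outcomes are correlated.* Holm does not use correlation. In the simulations the gain is, if anything, slightly smaller when correlation is higher.
- *That power rises to the high 80s or above.* That needs all 30 effects to be real. Section 9 itself describes the earlier evidence as conflicting.
- *That the sample-size basis is untouched.* Holm's first step is the same as a correct Bonferroni, so Holm alone does not change n. Declaring two-sided tests does: 136 per group rather than 122 under the plan's method.
- *That 122 was computed at the wrong alpha.* The recalculation points the other way, to a correct alpha and a misprint. This is an inference; the G-Power output is not in the documents.

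**Conclusion.** The point holds in this form. The printed alpha is wrong by a factor of ten and, taken literally, allows a family-wise error of about 0.40 with independent tests (0.15 to 0.32 at correlations of 0.7 to 0.3). The intended rule is evidently single-step Bonferroni at 0.0017, which matches 122 per group only if one-sided; two-sided, power is about 74%. Holm at family-wise 0.05 is preferable under either reading: against the printed 0.017 it restores error control, and against a true 0.05/30 it adds about 0 to 5 points of power per effect with 1 to 20 true effects.

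The decimal and the sidedness are corrections the plan needs. Holm is a worthwhile improvement of small to moderate size. The sample-size figures follow the plan's own two-group calculation with a normal parent. Whether that is the right basis for a within-patient design is a separate question and does not affect this conclusion.

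**What to change.** 1. In 2c, replace 0.017 with 0.0017 (0.05/30) in both places, and state whether tests are one- or two-sided.
2. Restate the power. One-sided, 122 per group gives 80%. Two-sided, either report about 74% at 122, or use 136, which with the plan's dropout allowance means 136/0.85 = 160 enrolled. The IRB form marks the remaining activity as data analysis only, so restating the power is probably the only course still open.
3. In 2c, replace the single-step rule with Holm step-down adjustment of the p-values at family-wise 0.05 over the 30 tests. Insert the same rule in 3d as new text, since there is no correction there to edit.
4. List the 30 tests by outcome and time point, so that the family is fixed.

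Date the change and make it before outcome comparisons are run. The cost is a few sentences and one list. Holm needs no additional patients; only the choice of sidedness bears on sample size.

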**If No, explain what SLU will NOT participate in:**

**Please save frequently**

Page numbers from a sponsor's protocol/grant may be referenced in 3b, 3c, and 3d.

- b) **Describe all the procedures, from screening through end-of-study, that the human subject must undergo in the research project, including study visits, drug treatments, randomization and the procedures that are part of standard of care. Specify which procedures are for research and which are standard of care. Please note: The box below is for text only. If you would like to add tables, charts, etc., attach those files in the Attachment section (#16).**

a.) Patients will have (standard of care) Endoscopic Sinus Surgery.  
 b.) Each patient will receive a hemostatic agent in one nostril and nothing in the other nostril.  
 c.) Products will be placed in patients' post-operative sinus cavities at the end of the procedure according to company recommended instructions. Essentially all products placed in the middle meatus are allowed to remain there until absorbed or removed at a post operative visit on weeks 1, 2, and 6. Post-operative irrigations (Standard of Care) will remove much of the material. Any residual material is removed in the office on normal, (Standard of Care) post-operative debridement on weeks 1, 2, and/or 6.  
 d.) Subjects will provide subjective pre- and post-operative data, such as rating their pain, bleeding, obstruction, and discharge on days 0, 1, 2, 7, and 14 (Standard of Care).  
 e.) Patients will be given a questionnaire packet pre-operatively (Research Related). Questionnaires will include post-operative data on days 0, 1, 2, 7, and 14. They are asked to bring completed questionnaires on standard post-operative visits.  
 f.) The physician will record objective and subjective data (synechiae, edema, infection, granulations, and time spent debriding) upon regular reexamination of the sinuses after surgery, at post-operative visits on weeks 1, 3, and 6. All procedures are standard clinical care.  
 g.) Follow up visits will conform to standard clinical care; patients will be seen in the physician's clinic.

**Protocol Title:** Analysis of hemostatic agents compared to physiologic hemostasis

---

clinic.

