- c) If the proposed study is a clinical trial where a drug, vaccine, device or other treatment is compared to a placebo group or comparison treatment group, what are the guidelines or endpoints by which early decisions regarding efficacy or lack of efficacy can be made? For example, it may be reasonable to stop enrollment on a study when efficacy has already been clearly demonstrated, to avoid unnecessary enrollments of additional subjects. Alternatively, it may be reasonable to stop enrollment when it is clear that efficacy will never be demonstrated, given the statistical power of the study as designed. Describe the guidelines that are in place to assist in making these determinations, if relevant to the proposed study.

If side effects or discomforts do occur, [name] and/or [name] will try to minimize and treat these by irrigating the treated sinus with saline to remove the Arista, Nexfoam, Sinufoam, Nasopore, Posiseq, or Posiseq X.

- d) Describe how data analysis will be performed (statistical tests, methods of evaluating data) and indicate the smallest group/unit for which separate reporting will occur. For studies involving a questionnaire, if data and reliability information are available, please describe or provide references. For full board, unfunded studies describe sample size determination and power analysis. If none, please justify.

Means and standard deviations will be obtained for data collected from patients and the physician. These outcomes will be used for comparative evaluation of hemostatic agents (n=144) against no therapy. Statistics will include descriptive statistics and a non-parametric ANOVA comparing the questionnaire patient data and the physician data followed by Post-hoc multiple comparisons.

Please save frequently

- e) State if deception (including incomplete disclosure of study purpose/procedures) will be used. If so, describe the nature of the deception and provide a rationale for its use. Also, describe debriefing procedures or justify a waiver of the requirement to debrief. NOTE: for studies using deception, an alteration of consent must be justified in the Informed Consent section of the protocol (#13) and the debriefing script/statement must be uploaded in the Attachments section (#16). See IRB Deception Guidelines.

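### Section 2c prints the Bonferroni alpha as 0.05/30 = 0.017; the quotient is 0.00167, and the plan's own 122 per group does not follow from 0.017

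*Combined protocol and SAP*

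**What the plan says.** Section 2c (study design) says "we calculated a Bonferonni correction to set the alpha for the analysis at 0.017" and shows the derivation as "alpha originally at .05 divided by the number of tests = .05/30 = 0.017". It then carries the same value into the sample size: "Given alpha at 0.017 and Power at 0.80", using the two-group Wilcoxon-Mann-Whitney test in G-Power to detect d = 0.5. The result is 244 in total, "122 in the control group, 122 in the hemostatics group". Because each patient supplies both nostrils, this is halved to 122 patients, and a 15% dropout allowance brings enrolment to 144. Neither the sidedness of the test nor the parent distribution is given.

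Section 3d (data analysis) plans descriptive statistics and "a non-parametric ANOVA comparing the questionnaire patient data and the physician data followed by Post-hoc multiple comparisons". It states no significance level and no adjustment method.

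**The concern.** The division is wrong by a factor of ten, in the direction that loosens the test. The value is not confined to planning, since section 2c sets it as the alpha for the analysis. No primary endpoint is named in the objectives (2b), design (2c) or analysis (3d) sections, so this correction is the only stated protection against false positives over many outcomes and days. If the analyst applies 0.017 to 30 comparisons, the family-wise error is no longer held at 5%.

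The printed alpha, power, effect size and sample size also cannot all be true together, so the paragraph does not show which alpha the sample size was built on.

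**Working it through.** **1. The quotient.** Inputs from section 2c: 0.05 and 30 tests. 0.05/30 = 0.001667. The printed 0.017 corresponds to a divisor of 0.05/0.017 = 2.9, that is, 3 rather than 30.

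**2. Which alpha gives 122 per group?** Inputs from section 2c: two-group Wilcoxon-Mann-Whitney, equal groups, d = 0.5, power 0.80. Method: asymptotic relative efficiency (A.R.E.) with the noncentral t. With n per group, m = n × A.R.E., df = 2m − 2, noncentrality = d√(m/2), and the critical value is the t quantile at 1 − α (one-sided) or 1 − α/2 (two-sided).

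Reproducing the plan's figure with α = 0.05/30, one-sided, normal parent (A.R.E. = 3/π):
- m = 122 × 0.955 = 116.5; df = 231.0; noncentrality = 0.5 × √58.25 = 3.816; critical t = 2.966.
- Power = 0.801. At 121 per group it is 0.797, so 122 is the smallest n that reaches 0.80.

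At the printed 0.017 the same 122 per group would have power 0.953 one-sided or 0.920 two-sided, not 0.80.

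Smallest n per group for 80% power (one-sided / two-sided):

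| Parent (A.R.E.) | α = 0.017 | α = 0.00167 |
|---|---|---|
| Normal (0.955) | 75 / 89 | **122** / 136 |
| Logistic (1.097) | 66 / 78 | 107 / 119 |
| Laplace (1.5) | 48 / 57 | 78 / 87 |
| Minimum (0.864) | 83 / 99 | 135 / 150 |

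No entry in the 0.017 column reaches 122.

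**3. Could 30 be a slip for 3?** At 0.05/3 = 0.01667 with a normal parent, n is 76 one-sided or 90 two-sided, again not 122.

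**4. Is 30 a plausible count?** Section 2c lists 4 symptoms on 4 days and 4 physician measures at 2 visits: 16 + 8 = 24. Section 3b has patients "rating their pain, bleeding, obstruction, and discharge on days 0, 1, 2, 7, and 14" and the physician recording "synechiae, edema, infection, granulations, and time spent debriding" at three visits: 4 × 5 + 5 × 3 = 35. Section 3b's days and measures combined with section 2c's two visits give 4 × 5 + 5 × 2 = 30. The questionnaires are attachments outside the text, so 30 is taken as the plan states it. All of these counts are far from 3.

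**5. Family-wise error if every null is true.** For k independent tests it is 1 − (1 − α)^k; the Bonferroni bound is kα.
- k = 30, α = 0.017: 1 − 0.983^30 = 0.402; bound 30 × 0.017 = 0.51.
- k = 30, α = 0.00167: 0.049; bound 0.05.
- k = 24 and 35 (independent): 0.337 and 0.451 at 0.017; 0.039 and 0.057 at 0.00167.

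The documents give no correlation between outcomes. Assuming equicorrelated normal test statistics, k = 30, α = 0.017:

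| Correlation | 0.3 | 0.5 | 0.7 | 0.9 | 0.95 |
|---|---|---|---|---|---|
| Two-sided | 0.319 | 0.233 | 0.150 | 0.070 | 0.049 |
| One-sided | 0.270 | 0.195 | 0.128 | 0.063 | 0.045 |

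**6. Enrolment.** 122/0.85 = 143.5, so 144, as the plan says.

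**The case against.** The strongest reply is that this is a visible slip. The operands 0.05 and 30 stand beside the wrong result, so a careful analyst would recover 0.00167, and the sample size seems to have been run at the right value. That is fair as far as it goes, but the value is printed three times, once expressly for the analysis, and section 3d offers nothing to override it.

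Four narrower points stand in part:
- **Enrolment.** That it is unaffected depends on a one-sided, normal-parent calculation. Two-sided with a normal parent, the plan's own method needs 136 per group, and 136/0.85 = 160 enrolled. A one-sided reading is not self-evident, because section 1a raises possible harm from absorbable packing. Two-sided with a logistic parent gives 119, so 122 is a good fit to the one-sided normal case but not proof of it.
- **Test count.** 0.00167 is right only for 30 tests. With 35 the bound is 35 × 0.00167 = 5.8%.
- **What is being tested.** Section 2c powers a two-group rank test, whereas section 3d plans a non-parametric ANOVA with post-hoc comparisons. The documents do not say which of these make up the 30.
- **Size.** Repeated ratings from the same patients are unlikely to be independent, so 40% lies at the high end of the range and should not be read as the expected value.

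None of this rescues 0.017.

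**Conclusion.** The concern holds, and the point must be fixed. The printed alpha is ten times the quotient it claims to be, and no sidedness or parent distribution tried reconciles it with 122 per group at 80% power. For 30 tests at 0.017, the family-wise error runs from 40% (independent) down to about 7% (correlation 0.9, two-sided), and drops just under 5% only near 0.95. At 0.00167 it is at most 5% under any correlation. The error figures assume that all 30 nulls are true and that the analyst uses the printed value. The arithmetic error and the mismatch with 122 need neither assumption. That the sample size was computed at 0.00167 is a well-supported inference, not something the documents state.

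**What to change.** - In section 2c, replace 0.017 by 0.00167 at all three places.
- In section 3d, state that threshold and list the 30 tests it covers, saying whether they are omnibus tests, post-hoc contrasts or both. If the list comes to a different number k, use 0.05/k.
- State the sidedness and parent distribution behind the 122. If the calculation was one-sided with a normal parent, enrolment stays at 144. If it was not, restate the power.
- Label any restated power of 80.1% (one-sided) or 73.6% (two-sided) at 122 per group as the figure for two independent groups with a normal parent. It is not the power of this trial, where "Each patient will receive a hemostatic agent in one nostril and nothing in the other nostril"; that depends on a within-patient correlation the documents do not give.
- The Expedited Paragraphs section (item 8c) marks the remaining work as data analysis only. Date the correction before outcome results are examined, or disclose that they already have been.

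The cost is wording in two sections, with no new patients or data on the one-sided reading. The downside is a stricter threshold than the one printed. For 122 pairs, two-sided, with d = 0.5 on the raw scale, standardised difference 0.5/√(2(1 − ρ)) and A.R.E. 3/π, power falls from 92% to 72% at an assumed within-patient correlation ρ of 0, from 97% to 85% at 0.2, and from 99.8% to 98% at 0.5.
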